4.0 Treatment plan

4.1 Overview

This will be a phase II, non-randomized trial to determine the efficacy and safety of the combination of Eribulin, and lenvatinib in patients with metastatic breast cancer, non-small cell lung cancer and sarcoma. Treatments will be given in cycles of 3 weeks (21 days) and staging scans(CT Scans) will be performed every 2 cycles. Bone scans and MRI brain will be optional. Toxicity assessment will take place after each cycle.

Eribulin will be administered on cycle days 1 and 8; lenvatinib is an orally administered medication which will be given daily throughout each cycle (on cycle 1 lenvatinib will be started on day 2). On days when both drugs are administered, Eribulin will be administered immediately prior to lenvatinib.

Patients will be followed after treatment discontinuation until disease recurrence or death. An evaluable patient for toxicity is any patient who has received at least 1 dose of any of the study drugs. An evaluable patient for efficacy is any patient who has received at least 2 cycles of therapy.

There will be a safety run-in phase. Ten patients will receive lenvatinib at 20 mg daily and Eribulin at 1.4 mg/m² day 1 and day 8 of a 21 day cycle. Eribulin will be given on day 1 and lenvatinib at 20 mg daily will be started on day 2. After completion of 1 cycle of therapy for the first 10 patients the PI will have a teleconference with the medical team at EISAI and decide whether to continue at the same dose or increase the dose to 24 mg daily of lenvatinib and Eribulin at 1.4 mg/m² day 1 and day 8 of a 21 day cycle.

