4.2 Study Drug Administration

Eribulin

Eribulin will be administered intravenously (IV) on days 1 and 8 of each cycle at a dose of 1.4 mg/m² over a 2-5 minute time period; on cycle day 1 in the Phase II portion of the trial; this will be immediately prior to Lenvatinib administration. Eribulin will be administered to the patient in the clinic (for drug preparation instructions, see section 7.0). Each cycle will last 21 (+/- 3) days. Laboratory tests will be performed within 2 days prior to days 1 and 8 of all cycles to assess toxicity and confirm that it is safe to proceed with treatment (see Section 7.0 for a complete listing of assessments). The dose of Eribulin will be calculated based on the BSA at study entry and *should only be recalculated if there is >10% change in body weight from baseline*. The actual body weight will be used for these calculations.

Lenvatinib

Lenvatinib will be self-administered by patients orally once a day during the study period. Patients will self-administer lenvatinib at home, except on study visit days. On these visit days, patients should take lenvatinib after chemotherapy is administered. Patients will be instructed to take each dose orally once daily, with or without food, starting on day 2 of cycle 1. The capsules should be swallowed whole without chewing, dissolving, or opening them. Patients should be instructed to take their dose of study drug at the same time each day. If the usual dosing time is missed, the patient should take the dose that day as soon as they remember as long as this is within 12 hours of the usual time the patient takes the dose. If it has been over 12 hours then this will be considered a missed dose. Patients should not make up missed or vomited doses; dosing should resume on the next calendar day unless otherwise instructed. Patients will be given a medication diary to record all doses taken, missed/skipped, or vomited. This diary will be reviewed with study personnel prior to dispensing medication for the next cycle.

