5.3.4 Endpoint Assessment

The overall response rate (ORR) will be defined as response after scans assessed after two cycles of therapy (1 cycle = 3 weeks). Clinical response will be assessed by the treating physician as outlined above. All patients who are on study after 2 cycles will be considered evaluable for the response endpoints.

Progression-free survival (PFS) will be defined as the time from the first study treatment to the first occurrence of progression or death. All patients who receive at least one dose of each drug will be evaluable for this endpoint.

Toxicity will be assessed NCI CTCAE v 4.03. The incidence, nature, and severity of adverse events will be determined. All patients who receive at least one dose of study drug will be considered evaluable for toxicity and safety endpoints.

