8.0 Statistical Considerations

8.1 Proposed sample size

8.1.1 Safety run in phase

The number of subjects in the safety run-in phase will be 10. In the phase II trial the number of patients will be 30. Three patients will receive lenvatinib at 20 mg qd and Eribulin at 1.4 mg/m² day 1 and day 8 of a 21 day cycle. Eribulin will be given on day 1 and lenvatinib will be started on day 2. If no DLTs are experienced, then the Phase II trial will be initiated at a dose of 24 mg daily of lenvatinib and Eribulin at 1.4 mg/m² day 1 and day 8 of a 21 day cycle. If there is a DLT, then three more patients will be treated at that dose level. If no more DLTs are observed, then the phase II trial can commence at lenvatinib dose of 20 mg qd and Eribulin at 1.4 mg/m² day one and day 8 of a 21 day cycle. If there is another DLT, then there will be a dose reduction of lenvatinib to 14 mg daily.

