4. results in a persistent or significant disability/incapacity;
5. results in a congenital anomaly/birth defect; or
6. based upon appropriate medical judgment, may jeopardize the subject's health and may require medical or surgical intervention to prevent one of the other outcomes listed in this definition

Unanticipated Problems Involving Risks to Subjects or Others Definition: Unanticipated problem involving risk to subjects or others includes any incident, experience or outcome that meets all of the following criteria:

unexpected (in terms of nature, severity, or frequency) given (a) the research procedures that are described in the protocol-related documents, such as the IRB-approved research protocol and informed consent document; and (b) the characteristics of the subject population being studied (note: the unfounded classification of a serious adverse event as "anticipated" constitutes serious non-compliance);
definitely related or probably related to participation in the research; and
suggests that the research places subjects or others at a greater risk of harm (including physical, psychological, economic, or social harm) than was previously known or recognized

Reporting Requirements

For this study, the Master Adverse Events Documents collected on patients for this protocol will be reviewed by the Principal Investigator on a monthly basis to determine if a serious safety problem has emerged that result in a change or early termination of a protocol such as:

- dose modification,
- suspending enrollment due to safety or efficacy, or
- termination of the study due to a significant change in risks or benefits.

The PI will provide the DSMB #2 with the monthly findings for discussion and review during their meetings.

Serious adverse events will be revised as they occur to determine if a DLT and the MTD has been reached. Adverse events and serious adverse events from all sites will be reviewed by DSMB#2 to determine if it is appropriate to escalate to the next dose level prior to opening the next cohort or determine that dose expansion at the current dose level is warranted.

For this protocol the number, frequency, and severity of adverse events and dose-limiting toxicities (DLTs) will be recorded (as defined by the NCI Common Terminology Criteria for Adverse Events or CTCAE v 4.03). The MTD will be defined as the dose level at which ≤ 1 (out of 3 or 6 patients) exhibit a DLT.

Dose-Limiting Toxicity (DLT) and Maximum Tolerated Dose (MTD)

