DLT evaluation will occur weekly for the first cycle (1 cycle = 21 days).

Any enrolled and treated patient should be evaluated for DLT purposes.

The DLT period as a whole will be the first cycle of treatment. (Adverse events, however, will continue to be collected for the duration of treatment).

In general, a non-hematologic DLT is defined as any Grade ≥ 3 toxicity, and a hematologic DLT is defined as any Grade ≥ 4 toxicity, both by CTCAE v4.03 criteria.

In addition, the following criteria and exceptions apply:

- ANC $< 500/\text{mm}^3$ for > 7 days despite GCSF support is a DLT.
- Platelet count $< 20,000/\text{mm}^3$ for more than 3 days that is considered drug-related is a DLT.
- For nausea, vomiting, or diarrhea, patients must have Grade 3 or 4 toxicity that persists at this level despite use of optimal symptomatic treatment (per local institutional guidelines), in order for these to be considered a DLT.
- Grade 3 thromboembolic events are not considered DLT.
- Any Grade 3 rash that resolves to Grade ≤ 2 within a 10 day period (including with symptomatic treatment) will not be considered a DLT.
- Cases involving hyperbilirubinemia that is primarily indirect, and considered not reflective of underlying liver disease (ie, resulting from transfusion of red blood cells), will not be considered a DLT.
- A DLT must be attributed to one of the two investigational drugs. A “drug-related toxicity” includes as events, any toxicity considered related, probably related, or possibly related to study drugs. Toxicities clearly not related to the drug, such as disease progression, environmental, unrelated trauma may not be considered “drug related toxicity”

- As per the Mays Cancer Center DSMP, any protocol modifications, problematic safety reports, unanticipated problems, and suspension or early termination of a trial must be reported to the DSMB #2 and all members of the research team at UT Health San Antonio and all affiliate sites. Furthermore, the PI of this study will promptly notify all study affiliates, the UT Health San Antonio IRB, the Mays Cancer Center DSMC, and the FDA via a FDA Form 3500Aa written IND safety report of any adverse events that are either serious and/or unexpected. Suspension and early termination of a trial must also be reported immediately to the Director of Quality Assurance who will promptly notify the sponsor and the UT Health San Antonio IRB.

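### The DLT set is every treated patient with no minimum exposure to the combination, so patients who leave cycle 1 without a DLT pull the run-in DLT rate down

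*Combined protocol and SAP*

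**What the plan says.** All references are to the combined protocol and SAP.

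- **Who is in the DLT set.** Appendix III, under Dose-Limiting Toxicity and Maximum Tolerated Dose: "Any enrolled and treated patient should be evaluated for DLT purposes".
- **Window.** Same place: "The DLT period as a whole will be the first cycle of treatment", which is 21 days.
- **What counts.** Same place: a DLT has to be attributable to a study drug. Events clearly due to something else, such as progression, may be excluded.
- **MTD rule.** Appendix III, Reporting Requirements: at most one patient may have a DLT, with the denominator given as "out of 3 or 6 patients) exhibit a DLT".
- **Start of lenvatinib.** Section 4.1: "on cycle 1 lenvatinib will be started on day 2". Section 4.2 agrees ("starting on day 2 of cycle 1").
- **General safety set.** Section 4.1: "An evaluable patient for toxicity is any patient who has received at least 1 dose of any of the study drugs". Section 5.3.4: "All patients who receive at least one dose of study drug will be considered evaluable for toxicity and safety endpoints".
- **Other endpoints.** Section 4.1 asks for two cycles before a patient is evaluable for efficacy. Section 5.3.4 asks for a dose of each drug for PFS.
- **Dose rule, first account.** Section 8.1.1 starts with three patients: "If no DLTs are experienced, then the Phase II trial will be initiated at a dose of 24 mg daily of lenvatinib". One DLT leads to three more patients.
- **Dose rule, second account.** The Synopsis and Section 4.1 describe ten patients, then a teleconference once they have completed a cycle. No numerical DLT threshold is given.
- **Use of the result.** Section 8.1.2 says the 30 phase II patients are treated at the MTD.
- **Outcome.** The note under the lenvatinib dose table in Section 4.3 records that, on the toxicity data of the first ten patients, the starting dose was not raised to 24 mg.

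**The concern.** Counting everyone who received a dose is the usual choice for listing adverse events. For a DLT rate it works the other way. The question is how often patients exposed to the combination have a DLT in cycle 1, and a patient who never took lenvatinib, or took little of it, says little about that.

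Under the Appendix III sentence such a patient is still in the set. If they left for progression, withdrawal or another reason unrelated to drug toxicity, there is no attributable event to score. The denominator grows and the numerator does not.

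Partial exposure matters as well as none. Section 7.2 gives a median of 16 days to new or worsening hypertension on lenvatinib, with 44% at Grade 3. Hypertension is not among the listed DLT exceptions. With a day-2 start, that median falls near day 17 or 18 of a 21-day window. Those data come from another population at 24 mg, but they show why one or two weeks on drug is not a complete DLT-free observation.

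At stake are the reported run-in DLT rate and the description of the phase II dose as the MTD. Early exits are plausible in stage IV disease with ECOG 0–2 and up to four prior regimens.

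**Working it through.** **1. The plan's own figure.** The only operating characteristics in the plan are for phase II (Section 8.1.2: N = 30, reject at 10 or more responses). The exact binomial gives alpha 0.0611 at a response rate of 0.20 and power 0.8237 at 0.40. Both match the plan and are not affected by this point. The plan gives no operating characteristics for the DLT or MTD rule.

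**2. Assumptions.** Let p be the DLT probability for a fully exposed patient and d the share who leave without an observed DLT. The documents give neither. I use p from 0.2 to 0.5 and d from 0 to 0.3. Leaving early is taken as unrelated to DLT risk.

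**3. The 3-then-6 rule in Section 8.1.1.** A level with no DLT in three patients is not expanded, so

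P(at most 1 DLT in 3 or 6) = (1−p)³ + 3p(1−p)⁵.

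Under the all-treated denominator, p is replaced by p(1−d).

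| p | d = 0 | d = 0.1 | d = 0.2 | d = 0.3 |
|---|---|---|---|---|
| 0.2 | 0.709 | 0.752 | 0.793 | 0.834 |
| 0.3 | 0.494 | 0.557 | 0.622 | 0.687 |
| 0.4 | 0.309 | 0.378 | 0.454 | 0.536 |
| 0.5 | 0.172 | 0.234 | 0.309 | 0.397 |

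At p = 0.3 the expected observed rate falls from 0.30 to 0.27, 0.24 and 0.21. P(0 of 3) = (1−p)³ rises from 0.343 to 0.389, 0.439 and 0.493.

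**4. Exactly one of the first three unexposed.** Assume that patient has no DLT risk and any further three patients are fully exposed. Then P = (1−p)² + 2p(1−p)(1−p)³. At p = 0.33:

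- all three exposed: 0.67³ + 3(0.33)(0.67⁵) = 0.301 + 0.134 = 0.434;
- one unexposed: 0.67² + 2(0.33)(0.67⁴) = 0.449 + 0.133 = 0.582.

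**5. Ten-patient run-in with two uninformative patients.** Three DLTs are 3/8 = 37.5% among informative patients but read as 3/10 = 30%. Two DLTs are 2/8 = 25% but read as 2/10 = 20%.

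**6. Search for a rule that already deals with this.** No section sets a minimum exposure, a replacement rule or a scoring rule for early leavers. Section 4.1 ties the teleconference to completion of a cycle, which fixes timing and not who is evaluable. Appendix III collects adverse events until 30 days after the last dose, which extends observation but does not supply exposure.

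**The case against.** **The dose decision is already made.** This stands. The Section 4.3 note records no increase to 24 mg. A reader might infer that the diluted denominator led to an unsafe escalation, but the documents show that none took place. A new definition now may also be post hoc and would have to be labelled so.

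**The plan never says that an early leaver is DLT-free.** This also stands. A reader might take it as a written rule, but it is an inference from evaluating everyone on a yes/no outcome in 3 or 6 patients without replacement. A patient who leaves because of a qualifying drug toxicity still counts as a DLT.

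**The 3-or-6 rule may not be the one used.** The Synopsis, Section 4.1 and the dose-table note describe ten patients and a judgement of tolerability. Under that account the denominator crosses no boundary, so the probabilities in steps 3 and 4 only illustrate the written rule. Dilution of the reported rate arises with 3, 6 or 10.

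**Exits may be rare.** Life expectancy must exceed 12 weeks and the first scan follows cycle 2, so exits for disease within 21 days are possible but unquantified. An eribulin-only patient also has some DLT risk, because a DLT may be attributed to either drug. Setting it to zero in step 4 overstates the effect.

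**An exposure requirement brings its own selection.** If it demanded both eribulin doses, it would drop patients whose day-8 dose was omitted for toxicity below the DLT level. That exclusion would be informative, so the definition has to keep them.

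**Conclusion.** The point holds as a bias in the reported run-in DLT rate and in the MTD statement, in the direction of tolerability. It rests on the written all-treated rule, the day-2 start of lenvatinib, the attribution requirement and the absence of a replacement rule.

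Its size cannot be fixed from the documents and is zero if nobody left early. For orientation, the chance of meeting the MTD definition rises from 0.49 to between 0.56 and 0.69 at p = 0.30 with 10% to 30% early exits. It rises from 0.43 to 0.58 at p = 0.33 if one of the first three is unexposed and carries no DLT risk. In a run-in of ten, the example is 30% reported against 37.5%.

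A fixed six-patient binomial at p = 0.33 gives a baseline of 0.36. That is not the figure for this rule, which does not expand a level with no DLT in the first three.

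**What to change.** 1. Replace the Appendix III sentence with a DLT-evaluable set: patients who had a DLT in cycle 1, or who received at least a minimum exposure to both drugs and were observed through day 21. The sponsor sets the minimum.
2. State that patients whose doses were omitted or reduced because of drug-related toxicity stay evaluable.
3. Report the run-in DLT rate over this set with the all-treated rate beside it. If the set is defined after the run-in, say so. The treatment forms (Appendix IV) and the medication diary (Section 4.2) already hold the exposure data.
4. Keep every treated patient in the general safety set of Sections 4.1 and 5.3.4.
5. Reconcile the ten-patient run-in (Synopsis, Section 4.1) with the 3-or-6-patient rule (Section 8.1.1, Appendix III), so that the denominator behind the MTD statement is clear.

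The cost is one definition, one table row and the reconciliation. The downside is that the DLT rate may look less favourable and rests on fewer patients.

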2.2 Clinical studies with Lenvatinib

Phase 1 trials

In phase 1 and 2 studies, oral lenvatinib exhibited antitumor activity against a variety of tumor types.²⁰ In a phase 1 trial conducted by Molina et al, with Lenvatinib and everolimus in the management of metastatic renal cell cancer, twenty patients (mean 58.4 years) received lenvatinib [12 mg (n = 7); 18 mg (n = 11); 24 mg (n = 2)] plus everolimus 5 mg. MTD was established as once daily lenvatinib 18 mg plus everolimus 5 mg. The most common treatment-related treatment-emergent adverse events (all dosing cohorts) were fatigue 60 % (Grade ≥ 3 : 10 %), mucosal inflammation 50 %, proteinuria (Grade ≥ 3 : 15 %), diarrhea (Grade ≥ 3 : 10 %), vomiting (Grade ≥ 3 : 5 %), hypertension, and nausea, each 40 %. In MTD and lowest-dose cohorts (n = 18), best responses of partial response and stable disease were achieved in 6 (33 %) and 9 (50 %) patients, respectively.

In a phase 1 study by Boss et al²¹, Eighty-two patients received Lenvatinib in dose cohorts from 0.2 to 32 mg. Dose-limiting toxicities (DLTs) were grade 3 proteinuria (two patients) at 32 mg, and the MTD was defined as 25 mg. The most frequently observed cumulative toxicities (all grades) again noted were hypertension (40% of patients), diarrhea (45%), nausea (37%), stomatitis (32%) and vomiting (23%). Seven patients (9%) had a partial response and 38 patients (46%) had stable disease as best response. Lenvatinib has dose-linear kinetics with no drug accumulation after 4 weeks' administration.

Another Phase I dose-escalation study and biomarker analysis of E7080 in patients with advanced solid tumors by Yamada et al²², twenty-seven patients (median age 53 years, performance status 0/1) were enrolled. E7080 was escalated from 0.5 to 1, 2, 4, 6, 9, 13, 16, and 20 mg bid by conventional 3-patient cohorts. During cycle 1, no grade 3/4 toxicity was observed up to 13 mg bid. DLTs included grade 3 AST/ALT increase in 1 patient at 16 mg bid and grade 3 platelet count decrease in 2 patients at 20 mg bid. The MTD of 13 mg bid was determined. After repeated doses, C(max) and area under the plasma concentration-time curve increased in a dose-dependent manner. After 14 days of treatment, c-kit(+) CEPs and CECs significantly decreased in cycle 1, but c-kit(-) CEPs and CECs did not. Change from baseline in c-kit(+) CEC ratio in cycle 1 and baseline SDF1 α , c-kit(+) CEPs and c-kit(+) CEP ratio significantly correlated with the E7080 therapeutic effect.

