6.0 Study Parameters

Procedures	Screening & Baseline	Cycle 1	Every cycle ²	Every 2 cycles or at study termination	End of study visit ⁷	Follow-Up ⁶
Tissue procurement ¹	X			X ⁵		
Informed consent	X					
Eribulin administration			X (Days 1 & 8)			
Lenvatinib			X once daily (starting on day 2 of cycle 1)			
Medical history ³	X		X		X	
Physical exam ³	X		X		X	
CBC w/ diff	X ³		X		X	
Comprehensive chemistry panel	X ³		X			
TSH	X		X			
Serum pregnancy test	X					
EKG	X		X ¹⁰			
Blood draw for micro RNA assay ⁹		X			X	

Procedures	Screening & Baseline	Cycle 1	Every cycle ²	Every 2 cycles or at study termination	End of study visit ⁷	Follow-Up ⁶
Urine analysis ¹¹	X			X		
Imaging ⁸	X ⁴			X		
Toxicity assessment			X			
Biopsy				X ⁵		
Survival status						X

¹Archival tissue or a fresh biopsy will be required to procure tissue for study purposes. Biopsy does not need to be repeated for study purposes if archived tissue is available.

Tissue procurement is voluntary

²A cycle is defined as 3 weeks or 21 days (+/- 3 days). Eribulin will be given on cycle days 1 and 8 and lenvatinib starting on day 2 of cycle one and then continuously.

³Pre-study laboratory tests, medical history, and physical exam (including performance status and review of systems) must be completed within 28 days prior to registration.

Pre-study CBC and CCP will be repeated on day 1 prior to treatment administration.

⁴Pre-study imaging must be performed within 28 days prior to registration.

⁵At the initiation and completion of study treatment (or at the time of early withdrawal), tissue samples should be obtained for correlative studies. This is voluntary and will only be done on patients who consent to it.

⁶Patients will be followed every 6 months, at the time of routine clinic visit or via phone, until death, to document disease progression and survival.

⁷Within 30 days of last dose of study medications.

⁸Imaging modality is left to the discretion of the investigator. However the same imaging modality should be used every two cycles to assess disease status.

⁹Blood samples for microRNA assay will be collected on Cycle 1, Day 1 and at the end of treatment.

¹⁰Repeat EKG with every cycle in patients with congestive heart failure, bradyarrhythmias, or those who are taking drugs known to prolong the QT interval, including Class Ia and III antiarrhythmics.

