¹¹Lenvatinib may cause proteinuria. Patients with 2+ or greater urine dipstick reading should undergo further assessment with a 24-hour urine collection. If 24hr urine protein ≥ 2 g then suspend lenvatinib until it decreases to <2 g and dose reduce by one dose level. If nephrotic syndrome then permanently discontinue lenvatinib.

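### No urine test is required inside the cycle-1 DLT window, so the run-in DLT count does not systematically cover grade 3 or higher proteinuria

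*Combined protocol and SAP*

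**What the plan says.** **DLT rule.** Appendix III sets the window: "The DLT period as a whole will be the first cycle of treatment". It also states "In general, a non-hematologic DLT is defined as any Grade ≥ 3 toxicity", subject to attribution to a study drug. The qualifiers that follow concern blood counts, nausea, vomiting and diarrhea, thromboembolism, rash and indirect hyperbilirubinemia. Proteinuria is not among them.

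**Urine schedule.** In the section 6.0 table, the urine analysis row is marked at screening and in the column headed "Every 2 cycles or at study termination". Its cells for cycle 1 and for every cycle are empty. Blood count, chemistry and TSH are marked every cycle. Footnote 11 makes the dipstick the entry to further work-up: "Patients with 2+ or greater urine dipstick reading should undergo further assessment with a 24-hour urine collection".

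**Frequency of evaluation.** Appendix III promises more than the calendar shows: "DLT evaluation will occur weekly for the first cycle (1 cycle = 21 days". It names no tests. Section 4.1 says "Toxicity assessment will take place after each cycle", and section 6.0 marks toxicity assessment once per cycle. Section 4.2 adds laboratory tests before days 1 and 8 of each cycle, but the only schedule that lists assessments is the one in section 6.0.

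**Use of the count.** Appendix III defines the MTD by DLTs among 3 or 6 patients, section 8.1.1 ties the phase II dose to DLTs, and section 8.1.2 tests response at the MTD. Section 4.1 has the dose teleconference after ten patients complete cycle 1.

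**The concern.** A DLT count covers only what is looked for inside its window. Proteinuria is a laboratory finding, and under footnote 11 the 24-hour collection follows from a dipstick. If no dipstick is due in cycle 1, a patient with grade 3 proteinuria can finish the window recorded as free of DLTs without any departure from the calendar.

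The protocol's own background shows why this toxicity matters. Section 2.2 reports, for the single-agent study whose MTD was 25 mg: "Dose-limiting toxicities (DLTs) were grade 3 proteinuria (two patients) at 32 mg, and the MTD was defined as 25 mg". At stake is whether a DLT rate or MTD statement from the run-in can be read as covering proteinuria. Under section 8.1.1 a single DLT changes the next step, so one uncounted case is not negligible.

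**Working it through.** **Step 1: timing.** The inputs are a cycle of 21 days with an allowance of 3 days either way (section 6.0), a DLT window of one cycle (Appendix III), and an on-treatment urine test every two cycles (section 6.0).

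- Window closes: day 21; range 21 − 3 = 18 to 21 + 3 = 24.
- First required on-treatment urine test: 2 × 21 = day 42; range 2 × 18 = 36 to 2 × 24 = 48.
- Nominal gap: 42 − 21 = 21 days. Even the latest window end and the earliest urine test do not overlap: 36 − 24 = 12 days.

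The one scheduled exception is a patient who stops in cycle 1, because the same column covers study termination.

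**Step 2: is the table being read correctly?** The imaging row has the same pattern of marks as the urine row, and the synopsis and section 4.1 confirm that imaging is every two cycles. The empty cells are therefore not an artefact of how the table was extracted.

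**Step 3: rates in the documents.** All are for whole treatment, not cycle 1.

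- 11% grade 3, lenvatinib 24 mg, thyroid cancer trial (Appendix I, label section 5.5), over a median of 16.1 months on treatment (label section 6.1).
- 15% grade 3 or higher, lenvatinib plus everolimus, phase 1 (section 2.2).
- 2% grade 3, medullary thyroid phase II (section 2.2).
- 4% grade 3/4, melanoma phase II (section 2.2).

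**Step 4: assumed cycle-1 rates.** The documents give no onset time for proteinuria, so the cycle-1 rate must be assumed.

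- Low end: spread the 11% evenly over 16.1 months. With 30.4 days per month this is 16.1 × 30.4 ≈ 489 days, and 0.11 × 21/489 ≈ 0.0047, or about 0.5%.
- High end: 5%, which amounts to 5/11 ≈ 45% of the 11% arising in the first cycle.

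**Step 5: chance of at least one case among n patients**, 1 − (1 − p)^n:

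| Assumed p | n = 3 | n = 6 | n = 10 |
|---|---|---|---|
| 0.5% | 1.5% | 3.0% | 4.9% |
| 2% | 5.9% | 11.4% | 18.3% |
| 5% | 14.3% | 26.5% | 40.1% |

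For ten patients the range is about 5% to 40%. It treats patients as independent and supposes that no case is found by an unscheduled or termination test. Any such test lowers the chance that a case goes uncounted.

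**The case against.** Several stronger conclusions are tempting, and the documents do not support them.

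- **That the choice between 20 and 24 mg was compromised.** The note to Table 2 in section 4.3 records that, on the toxicity data of the first ten patients, the starting dose was not raised. No escalation followed from the gap.
- **That the first urine result always comes after the dose teleconference.** The call waits for ten patients to complete cycle 1. With staggered entry, early patients can reach day 42 before it. The synopsis also bases the decision on tolerability, which is wider than DLTs. Those results could inform the call, although they lie outside the DLT window.
- **That proteinuria cannot be detected in cycle 1.** Footnote 11 is not limited to scheduled dipsticks, a patient stopping early would be tested, and the weekly DLT evaluation could include urine. The accurate statement is that testing is not required.
- **That proteinuria is the toxicity that set the lenvatinib MTD in general.** It did so in the once-daily study, at 32 mg. The twice-daily phase 1 study in section 2.2 had AST/ALT and platelet DLTs. The once-daily study is the closer precedent for this trial's schedule, but this trial starts at 20 mg.
- **That a large bias has been shown.** The 11% accrued over many months at 24 mg, and two other trials report 2% and 4%. The direction of bias is plausible; its size is not established.

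It is also fair to say that a weekly cycle-1 DLT evaluation can coexist with a general assessment after each cycle, and that section 4.2 provides day 1 and day 8 laboratory tests. On that reading the calendar merely omits the weekly evaluation.

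What stands is the mismatch itself. The rule counts an event that the calendar does not require anyone to look for until the window has closed, and none of these routes makes a cycle-1 urine test mandatory for a patient who continues.

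**Conclusion.** The point holds as a gap between the DLT definition and the assessment calendar. It rests on the schedule alone and needs no assumed event rate. The run-in DLT count does not systematically cover grade 3 or higher proteinuria and may be biased low. The 5% to 40% figure is an illustration across assumed cycle-1 rates, not an estimate. What remains affected is the completeness of the DLT and MTD evidence at 20 mg. The absence of the weekly cycle-1 DLT evaluation from the calendar and section 4.1 is a second, smaller inconsistency. The matter should be corrected or disclosed, but it does not undermine the phase II response analysis.

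**What to change.** Reconcile Appendix III with sections 6.0 and 4.1:

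- Place a urine protein assessment for DLT-evaluable patients inside the DLT window, before DLT status is assigned, and state its timing. A mark under every cycle would not be enough, since it could be read as day 1. Allow for the 24-hour collection that a positive dipstick triggers. This need not change the urine schedule in later cycles or for other patients.
- Show the weekly cycle-1 DLT evaluation in the calendar and in section 4.1, and name the tests it includes.
- For run-in patients already past cycle 1 without a urine test, report that the DLT rate does not cover proteinuria.

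The cost is a calendar amendment, one dipstick at an existing visit and one sentence in the report. The downside is a few more 24-hour collections and possibly a slightly higher DLT count.
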